13.6 Exploratory Objectives

The 6 exploratory objectives include an examination of the duration of admission stay, the number of provider communications, use of intraoperative AED, seizure occurrence, modifications of AED administration and risk factors for post-MSR seizure.

13.6.1 Exploratory Objective: Duration of Admission Stay

For each patient accrued to this study, the duration of the initial admission stay for the MSR will be calculated as the time interval between the date of MSR and date of discharge. A Wilcoxon rank sum test will compare the combined AED groups versus the no AED group with respect to the distribution for the duration of the initial admission stay. Reasons for an extended initial stay greater than 2-3 days will be summarized by treatment group.

13.6.2 Exploratory Objective: Number of Provider Communications

The number of provider communications (email, telephone, or additional clinical visits) during the 30 days post-MSR will be determined for each patient. Within each group, the distribution of the total number of provider contacts will be summarized with a frequency distribution. Either a Wilcoxon rank sum test or a chi-square test will compare AED (combined) and no AED groups.

13.6.3 Exploratory Objective: Usage of Intraoperative AED

Whether or not intraoperative AED is administered will be assessed for each patient, and the proportion of subjects requiring an intraoperative AED will be calculated within each group. AED (combined) and no AED groups will be compared with respect to the percentage of subjects requiring an intraoperative AED with a chi-square test.

Details concerning the type and dose of AED will also be summarized descriptively.

13.6.4 Exploratory Objective: Seizure Occurrence

The percentage of patients experiencing post-MSR seizures will be assessed within each arm. A chi-square test will compare AED (combined) to no AED groups relative to this outcome.

In addition, the distribution of the number of seizures experienced over the 30 day period will be generated within each arm. A Wilcoxon rank sum test will compare AED (combined) and no AED groups with respect to the number of seizures reported.

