4 STUDY SCHEMA

5 BACKGROUND AND SIGNIFICANCE

5.1 Study Disease

Seizures are a debilitating complication of brain tumors. Aberrant and repetitive neuronal firing leads to the generation of seizures. Approximately 75% of patients with low grade tumors and 25% with high grade tumors suffer from seizures compared to 0.5-1% of the general population². Slower growing, low grade tumors are associated with higher epileptogenicity, while faster growing, high grade tumors are associated with seizures secondary to mass effect³. Higher seizure frequency has been associated with reduced cognitive function and Health-Related Quality of Life (HRQOL) and strips patients of driving privileges for 6 months on average in the US, thus affecting daily functional activities of living⁴. While surgery can be potentially curative of tumor-related seizures by resecting the nidus of seizure activity, it could also cause seizures due to irritation of the cortex, hemorrhage at the surgical site, and cerebral hypoxia and acidosis during surgery⁵.

The current guidelines recommend against peri-operative seizure prophylaxis in patients who have never had a seizure, and to taper Anti-Epileptic Drug (AED) therapy after the first post-procedure week^{6,7}. However, these guidelines were based on older generation AEDs [(Phenytoin (PHT), Phenobarbital (PBT), and Valproic Acid (VPA))] that were associated with significant side effects and drug-drug interactions. Since these guidelines were published in 2000, and reaffirmed in 2003 and 2008, newer generation AEDs have emerged with more favorable side effect profiles⁸. LCM, a third generation AED and LEV, a second generation AED, are both well tolerated with unique mechanisms of action.

Given the reduced risk of adverse event occurrence with newer AEDs, the clinical use of AEDs as prophylaxis has increased⁹; however, there have been no updated guidelines and there is a lack of clinical trial data to reflect this practice. LCM is US Food and Drug Administration (FDA) approved as adjunctive and monotherapy for partial-onset seizures and LEV is approved as adjunctive therapy^{10 11}. Their promising roles in brain tumor patients continue to be explored.

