7.1.8 Randomization

Upon consent, patients will be randomized in REDCap™ to receive either LCM, LEV, or no AED. Randomization will be stratified by suspected histologic grade (LGG vs HGG) based on MRI review by the treating neurosurgeon and/or neuro-oncologist. A stratified permuted block randomization algorithm will be used assign patients to treatment arms.

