9.1.2 Exclusion Criteria

1. Pregnant or need to breast feed during the study period (Negative urine β -HCG test required), or unable to maintain use of contraception while on study and for 1 month after the last dose of AED;
2. Patients already on AED(s) specifically to treat seizures will be excluded. Those patients taking AEDs for any diagnosis other than seizures will be included (e.g. Gabapentin for neuropathic pain, Topiramate for migraine, benzodiazepines as sleeping aid, etc). Patients taking AEDs for seizure prophylaxis and without clear history of seizures will be included;
3. Known history of epilepsy/seizure disorder;
4. Known history of dependency/abuse of psychopharmaceuticals, alcohol, illicit drugs or narcotics;
5. Any significant medical or psychiatric illness that cannot be adequately controlled with appropriate therapy or would compromise the patient's ability to tolerate therapy, per the discretion of the treating investigator;
6. Known allergy to LCM or LEV.

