13.4.2 Statistical Hypothesis, Model, and Method of Analysis

Though the percentage of patients who are re-hospitalized or have an emergency room visit during the 30 days post-MSR will be calculated within each treatment group, the primary comparison will combine outcome observed within the LCM and LEV arms. The statistical comparison will assess the impact of AED (LCM or LEV) relative to no AED on this endpoint.

Let us define P1 and P2 as follows:

P1 = Percentage of patients treated prophylactically with AED (LCM or LEV) who are re-hospitalized or have an emergency room visit during the 30 days post-MSR

P2 = Percentage of patients not prophylactically treated (i.e. no AED) who are re-hospitalized or have an emergency room visit during the 30 days post-MSR

Given that current guidelines recommend against peri-operative seizure prophylaxis, we are interested in showing that AED is better than No AED, or $P1 < P2$, or $0 < P2 - P1$. Hence, the hypothesis we will be testing is:

$$H_0: \theta \leq 0 \text{ vs } H_1: \theta > 0$$

where $\theta = P2 - P1$. A one-tailed test using a large-sample Z test will be conducted given the directional hypothesis that is being posed.

With stratification for suspected grade (LGG vs HGG), the Cochran-Mantel-Haenszel test statistic will compare patients who do and do not receive AED with respect to the proportion of patients re-hospitalized or have an emergency room visit during the 30 days post-MSR.

An interim analysis will be conducted half way through the study to assess whether early study termination is appropriate. An O'Brien-Fleming boundary will provide guidance for making that assessment. This interim analysis will determine whether the hypothesis can be rejected or accepted at that time. See section 13.7 and 13.8 for further detail.

An intent-to-treat philosophy will be used in generating statistical analyses.

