13.5 Secondary objectives

This study has one secondary objective which is to assess the safety and tolerability of LCM and LEV.

Adverse events will be assessed according to the NCI Common Toxicity Criteria for Adverse Events (CTCAE) version 4. For each type of toxicity, the maximum grade experienced by the patient will be summarized with frequency distributions based upon all AESIs. Of particular interest are those adverse events of special interest (AESI), as defined in section [7.1.4](#), that occur within 30 days after MSR.

The percentage of patients experiencing any grade adverse events of special interest within 30 days of MSR will be summarized in each of the 3 treatment arms, and compared using chi-square tests. If AED is shown to have fewer re-hospitalizations or ED visits, then a pairwise comparison of LCM and LEV is of particular interest.

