13.6.6 Exploratory Objective: Risk Factors for Post-MSR seizure

Well-known risk factors predictive of seizure will be assessed (age, frontal/temporal/parietal tumor locations, cortical vs. subcortical location, tumor size, low grade vs. high grade tumor, extent of resection [GTR vs. sub-total resection (STR) vs. biopsy] ⁷¹⁻⁷⁷. Other potential risk factors such as tumor genetics will also be collected, such as, but not limited to: IDH1 mutation, TERT, ATRX, EGFRvIII. The association between each of these factors and the occurrence of post-MSR seizure will be examined within a logistic regression model.

Depending upon the prevalence of post-MSR seizures, a multivariate logistic regression analysis may be conducted that examines the joint effect of these factors, as well as treatment assignment and treatment interactions on outcome. To maintain validity and stability of such modeling, the number of predictors for consideration in a multivariable logistic model will be no more than 1 predictor for every 10 seizures.

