13.8 Sample Size

Eligible subjects will be randomized to one of 3 treatment arms (LCM, LEV, or no AED) using an allocation ratio of 1:1:2. Randomization will be implemented using a permuted block algorithm. Randomization will be stratified by suspected grade of glioma (high vs low grade) or brain metastasis..

The experience of subjects in the LCM and LEV groups will be combined to estimate the percentage of subjects with an ED visit or readmission within 30 days of MSR after seizure prophylaxis pre-surgery. That outcome will be compared to the same outcome observed among patients in the no AED group.

In designing this study, we have considered the following background information:

- In a recently conducted retrospective review of Duke’s experience with AEDs and MSR (Pro00047350 Descriptive and Cost Analysis of Post-procedure Anti-Epileptic Drugs in Malignant Glioma), the experience of patients newly diagnosed with malignant glioma and without prior seizure history or AED use was examined. Among those patients who were prophylactically treated with LEV before MSR, 12% of subjects were re-hospitalized or visited emergency room within 30 days post-MSR.
- Published literature indicates that the risk of post-MSR seizure in MG patients without AED prophylaxis ranges from 2.3% up to 35%, particularly in glioblastoma (GBM).^{75,77,78}

Therefore in designing the study we have assumed that the percentage of patients with re-hospitalization or ED visits within 30 days post-MSR is 12% in both the LCM and LEV groups. We have also designed the study to detect an increase in re-hospitalization or ED visits to 25% within the no AED group.

Additional assumptions for the power calculations include the following:

- One-tailed test conducted so that the overall type I error rate is 0.05. This type I error rate accounts for one interim analysis.
- Power = 80% under the alternative where the true outcome is 12% in the AE group (combined) and 25% in the no AED group.
- One interim analysis half way through the study that allows early termination with either acceptance or rejection of the null hypothesis.

Under these conditions, there is a need to randomize and follow 232 subjects for 30 days. An interim analysis as described in Section [13.7](#) will be conducted after 116 patients (SAS PROC SEQDESIGN).

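### Seizure occurrence and AESI are tested without the grade strata used at randomization; for seizure this makes the test somewhat conservative, with a small and uncertain loss of power

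*Protocol*

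**What the plan says.** Protocol 7.1.8: "Randomization will be stratified by suspected histologic grade (LGG vs HGG", judged on MRI before surgery. Protocol 13.8 words the factor differently: "Randomization will be stratified by suspected grade of glioma (high vs low grade) or brain metastasis".

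The primary analysis uses the factor. Protocol 13.4.2: "With stratification for suspected grade (LGG vs HGG), the Cochran-Mantel-Haenszel test statistic will compare patients who do and do not receive AED".

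Two other comparisons do not:
- Seizure occurrence, Protocol 13.6.4: "A chi-square test will compare AED (combined) to no AED groups relative to this outcome". The number of seizures is compared with a Wilcoxon rank sum test, also without strata.
- AESI, Protocol 13.5: the percentages "will be summarized in each of the 3 treatment arms, and compared using chi-square tests". The AESI list in 7.1.4 begins with seizure of any grade.

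On the link between grade and seizure, Protocol 13.6.6 includes "low grade vs. high grade tumor, extent of resection" in its list of recognised seizure risk factors, without effect sizes. Protocol 5.1 gives background figures: "Approximately 75% of patients with low grade tumors and 25% with high grade tumors suffer from seizures".

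Seizure occurrence is exploratory in the Protocol (Table 1) and a secondary objective in the SAP (section 3). The SAP text available for review defines outcomes and variables. Its later pages were not available, so this point concerns the Protocol's wording.

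**The concern.** Stratified allocation makes the groups nearly equal in grade mix, so differences between grades hardly contribute to the variance of the treatment comparison. An ordinary chi-square test still counts that between-grade variation. When grade predicts the outcome, its variance is too large, its true size falls below the nominal level and some power is lost.

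The consequence is a missed difference, not a false one. Neither endpoint has a power calculation, so there is no planned margin to absorb a loss. For a safety comparison, an undersized test leans towards finding no difference in harm. The plan also treats the same design factor in two ways, with no reason given.

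**Working it through.** **Plan's own figure.** The Protocol gives no power or error figure for these two tests. Its one design figure is N = 232 for the primary endpoint (12% vs 25%, one-sided 0.05, 80% power, one interim). Integrating the two-stage design with the stated boundaries (2.31015, 0.48887, 1.63351) gives an overall type I error of 0.0500. The required total is 230.1 with unpooled variance and 236.7 with pooled variance. So 232 reproduces, and it is used below as 116 vs 116 (allocation 1:1:2, the two AED arms combined).

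**Inputs not in the documents (assumed).** Low-grade share *w* from 10% to 50%; 30-day seizure rates without AED by grade, *p*L and *p*H; a common within-stratum odds ratio of 0.45; nominal two-sided 5%.

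**Size of the unstratified test.** With *p* = *w p*L + (1−*w*) *p*H,

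R = [*w p*L(1−*p*L) + (1−*w*) *p*H(1−*p*H)] / [*p*(1−*p*)]

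true two-sided size = 2[1 − Φ(1.96/√R)]

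At *w* = 25%:
- 75% vs 25%: R = 0.1875 / (0.375 × 0.625) = 0.80; size 2.8%.
- 35% vs 15%: R = (0.25 × 0.2275 + 0.75 × 0.1275) / (0.20 × 0.80) = 0.1525 / 0.16 = 0.953; size 4.5%.
- 20% vs 10%: R = (0.25 × 0.16 + 0.75 × 0.09) / (0.125 × 0.875) = 0.1075 / 0.1094 = 0.983; size 4.8%.
- No grade effect: R = 1; size 5.0%, nothing lost.

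**Power, by simulation (200,000 trials per row, N = 232, odds ratio 0.45).** Sizes are simulated and can differ slightly from the formula because counts are discrete.

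| Assumed rates, low vs high grade | Low-grade share | Chi-square size | Chi-square power | CMH power | CMH gain (points) |
|---|---|---|---|---|---|
| 75% vs 25% | 10% | 3.8% | 61.8% | 66.8% | 5.0 |
| 75% vs 25% | 25% | 2.8% | 61.1% | 69.8% | 8.7 |
| 75% vs 25% | 30% | 2.8% | 61% | 71% | 10 |
| 75% vs 25% | 50% | 2.8% | 65.7% | 74.1% | 8.4 |
| 35% vs 15% | 10% | 4.8% | 48.9% | 50.1% | 1.2 |
| 35% vs 15% | 25% | 4.5% | 53.9% | 55.4% | 1.5 |
| 35% vs 15% | 50% | 4.3% | 61.9% | 63.5% | 1.6 |
| 30% vs 10% | 30% | 4.3–4.4% | 45% | 47% | 2 |
| 20% vs 10% | 10% | 4.9% | 37.0% | 36.1% | −0.9 |
| 20% vs 10% | 25% | 4.7% | 40.1% | 39.8% | −0.3 |
| 20% vs 10% | 50% | 4.8% | 45.3% | 45.8% | 0.5 |

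CMH size was about 5.0% throughout. One further extreme case gives each grade one end of the 2.3% to 35% range in Protocol 13.8 (35% low grade, 2.3% high grade). The gain is then 5 to 6 points and chi-square size is 2.9% to 3.2%. That range is for malignant glioma and is not a contrast between grades.

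**Three-arm AESI test.** The same R applies with 2 degrees of freedom: size = exp[−5.991/(2R)]. R = 0.80 gives 2.4% and R = 0.953 gives 4.3%. These hold only if AESI rates differ by grade to that extent, which the documents do not say. Power was not simulated for three arms.

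**Do the 75% and 25% carry over?** They describe how many tumor patients have seizures at all. The trial counts seizures within 30 days of surgery and excludes patients with "Known history of epilepsy/seizure disorder". With a 30% low-grade share they imply 0.30 × 75% + 0.70 × 25% = 40% without AED, above the 35% top of the only no-prophylaxis range in the Protocol. They are an upper bound, not an expected value.

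**The case against.** The strongest reply is that an unadjusted test on a secondary and an exploratory endpoint, neither powered, is defensible. It does not inflate false positives, and at plausible rates it costs almost nothing. All of that stands and sets the weight of the point.

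A second reply is that Protocol 13.6.6 already allows a logistic model with grade, treatment and interactions. It is only a partial answer. The model is optional, covers seizure but not AESI, and allows one predictor per 10 seizures. With fewer than 20 seizures (20/232 = 8.6%, inside the quoted 2.3% to 35%), treatment and grade could not both enter.

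A reader might also draw three stronger conclusions that the documents do not support:
- That AESI as a whole depends strongly on grade. Seizure is the only item in the 7.1.4 list that the documents link to grade; the others are largely known drug side effects.
- That power losses near 10 points are to be expected. They require background prevalence to stand in for 30-day rates in a population without known seizure disorder.
- That the unstratified tests in 13.6.1 to 13.6.3 (length of stay, communications, intraoperative AED) should change as well. No dependence on grade is shown for those outcomes.

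**Conclusion.** The mismatch between stratified randomization and unstratified tests in Protocol 13.6.4 and 13.5 is real. For seizure occurrence the chi-square test is somewhat conservative, because the Protocol itself treats grade as prognostic. For AESI this holds only to the extent that AESI depends on grade, which is not documented beyond its seizure component.

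The likely effect is small: between about 1 point lost and 2 points gained by stratifying, with true size 4.3% to 4.9%, at moderate assumed contrasts. A gain of 5 to 10 points, with true size 2.8% to 3.8%, belongs to the 75% vs 25% upper bound. All power figures rest on the assumed rates, low-grade share and odds ratio of 0.45. This is a low-priority improvement in efficiency and consistency, not a threat to validity.

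**What to change.** 1. In Protocol 13.6.4, replace the chi-square test with a CMH test stratified by the randomization strata, and the Wilcoxon test on seizure counts with the van Elteren (stratified Wilcoxon) test.
2. In Protocol 13.5, use the CMH general-association test for the three-arm AESI comparison, to match the primary analysis.
3. Define the strata as implemented at randomization. Sections 7.1.8 and 13.4.2 have low vs high grade, while 13.8 adds brain metastasis; state whether metastasis is its own stratum or where those patients were placed. The primary CMH test needs this too.
4. Carry the same wording into the SAP if it is not already there, and leave 13.6.1 to 13.6.3 as they are.

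The cost is analysis code and the clarification in item 3. With no grade effect there is essentially no power cost; the worst case in the table was about 1 point, at 20% vs 10% with a 10% low-grade share.

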13.6.5 Exploratory Objective: Changes in AED Administration

The frequency of changes in AED dose, type of AED, addition or discontinuation of AED will be described.

13.6.6 Exploratory Objective: Risk Factors for Post-MSR seizure

Well-known risk factors predictive of seizure will be assessed (age, frontal/temporal/parietal tumor locations, cortical vs. subcortical location, tumor size, low grade vs. high grade tumor, extent of resection [GTR vs. sub-total resection (STR) vs. biopsy] ⁷¹⁻⁷⁷. Other potential risk factors such as tumor genetics will also be collected, such as, but not limited to: IDH1 mutation, TERT, ATRX, EGFRvIII. The association between each of these factors and the occurrence of post-MSR seizure will be examined within a logistic regression model.

Depending upon the prevalence of post-MSR seizures, a multivariate logistic regression analysis may be conducted that examines the joint effect of these factors, as well as treatment assignment and treatment interactions on outcome. To maintain validity and stability of such modeling, the number of predictors for consideration in a multivariable logistic model will be no more than 1 predictor for every 10 seizures.

13.7 Interim Analysis

After 116 accrued patients have completed their 30 day follow-up post-MSR, an interim analysis will be conducted. This analysis that is conducted halfway through the study will assess whether accrual could be terminated early and whether the null or alternative hypothesis could be accepted.

[figure not shown]
The O'Brien-Fleming boundaries that are used in the decision-making are defined in terms of a Z-statistic. Those boundaries are provided below for the interim and final analysis (SAS PROC SEQDESIGN).

Stage	Total N Accrued	Total Assigned to AED Groups	Total Assigned to No AED Group	Reject Null Hypothesis * if:	Accept Null Hypothesis ** if:
1	116	58	58	$Z > 2.31015$	$Z \leq 0.48887$
2	232	116	116	$Z > 1.63351$	$Z \leq 1.63351$

*Reject null hypothesis and conclude that AED better.

**Accept null hypothesis and conclude that AED is not better.

These boundaries are presented graphically below. The interim analysis occurs at the point on the x-axis labeled as (1), and the final analysis occurs at the point labeled as (2).

The standardized Z statistic presented in the boundaries above is a function of the following difference: Percent of no AED patients with re-hospitalization or ED visit – Percent of AED patients with re-hospitalization or ED visit. The denominator of the Z statistic is a measure of the variability of this difference.

- If the observed percentage of patients with re-hospitalization or ED visits is greater within the no AED group than in the AED group, then the Z statistic will be positive.
- If the observed percentage in the no AED group is less than that in the AED group, then the Z statistic will be negative.
- If there is no difference between groups in the observed percentage of patients with re-hospitalization or ED visits, then the Z statistic will be 0.

The dark blue region in the figure above is where one concludes that AED is better than no AED; whereas, the light blue region is where one concludes that AED is not better than “no AED” (i.e. they are the same or no AED is better). At the time of the interim analysis, the study will be terminated if $Z > 2.31013$ (i.e. observed percentage within the no AED group is much larger than that in the AED group) and the conclusion will be that AED treatment is better. Also at the time of the interim analysis, the study will be terminated if $Z \leq 0.48887$ (i.e. observed percentage within the AED group is greater than that observed in the no AED group, or about the same with AED or no AED) and the conclusion will be that AED treatment is not better. If the Z calculated at the time of the interim analysis is between 0.48887 and 2.31013, the remaining patients will be accrued to the study. At the time of the final analysis, the threshold for decision-making is $Z=1.63351$.

If the accrual is unbalanced at the time of the interim analysis, the boundaries stated here may need to be modified slightly.

Though the verb “terminated” is used above in the description of the monitoring rules, these rules should be viewed as guidelines for the determination of whether accrual should be terminated or not. Additional factors may be considered in the determination of whether accrual should continue after the interim analysis.

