5.2.9 Study Purpose and Rationale

The primary purpose of this study is to evaluate 30-day readmission rates and ED visits through randomizing subjects to "no AED" or to the 2 primary AEDs used in this patient population here at DUMC.

Current guidelines recommend against peri-operative seizure prophylaxis for patients with newly diagnosed brain tumors; however, they were based on older generation AEDs that were associated with severe toxicities and drug-drug interactions. In light of newer generation AEDs with more tolerable safety profiles, some neurosurgeons and neuro-oncologists prescribe AEDs to patients for prolonged periods of time after surgery, despite these guidelines; this has also been the practice here at DUMC. Given the lack of recommendation for AED prophylaxis in the peri-operative period by the neurosurgical guidelines, which is contrary to Duke's practice, and given the cost and potential side effects of AEDs, it was determined that it is now time to formally assess the impact and side effect profile of the use or not of AEDs. If determined that AED is necessary, this study will also attempt to evaluate the side effect profile of the commonly used AED at Duke (levetiracetam) versus a newer AED (lacosamide).

The question most relevant to Duke neurosurgeons is the rate of readmission and ED visits after a Maximum Safe Resection (MSR) (gross-total, sub-total or biopsy), a measurable patient outcome to their surgery. If there is benefit on these rates from having an AED, that would provide support for neurosurgeons to prescribe AEDs. If there is no difference in readmission rates/ED visits between those who did and did not receive an AED, then there would be much more support against AED prophylaxis. If the adverse side effects of the AEDs studied are significant, then there will be a greater consideration of risk to benefit.

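### Section 13.7 turns a non-significant one-sided superiority test into the conclusion that AED is no better than no AED, which a Z below the boundary does not establish

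*Protocol*

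**What the plan says.** Protocol section 13.4.2 sets θ = P2 - P1, the no-AED event rate minus the AED event rate. It tests H0: θ ≤ 0 against H1: θ > 0, one-tailed. No equivalence or non-inferiority margin appears in the text available.

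Section 13.7 attaches a conclusion to not rejecting H0 in three places:

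- The boundary table footnote reads "Accept null hypothesis and conclude that AED is not better".
- The description of the light blue region of the figure adds the gloss "i.e. they are the same or no AED is better".
- For an interim stop at Z ≤ 0.48887, "the conclusion will be that AED treatment is not better".

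At the final analysis, the same table row and region cover every Z ≤ 1.63351.

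The accept/reject vocabulary appears elsewhere too. Section 13.7 opens by asking "whether the null or alternative hypothesis could be accepted", section 13.4.2 says "This interim analysis will determine whether the hypothesis can be rejected or accepted at that time", and section 13.8 describes an interim look that "allows early termination with either acceptance or rejection of the null hypothesis".

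Section 13.7 closes with a caveat: "these rules should be viewed as guidelines for the determination of whether accrual should be terminated or not". Section 5.2.9 gives a negative finding a practical use. It begins "If there is no difference in readmission rates/ED visits between those who did and did not receive an AED" and goes on to say that the case against prophylaxis would then be stronger. It does not define no difference.

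**The concern.** The gloss is H0 put into words. A test that fails to reject H0 has not shown H0 to be true. It has failed to show a benefit at the chosen error rate. To claim that the groups are the same, the plan would need a margin or an interval criterion, and the available text has neither. To claim that no AED is better would need evidence in the opposite direction, and Z values well above zero also fall in the acceptance region.

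The closing caveat does not repair this. It concerns whether accrual stops, not what is concluded about the treatments.

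What is at stake is how the trial's own result is read. Section 5.2.9 says the outcome may affect local practice, while disclaiming any aim of changing the general standard. An inconclusive result reported in the words of section 13.7 would look like a finding against prophylaxis.

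**Working it through.** **Inputs.** From section 13.8: AED rate 12%, no-AED rate 25%, one-sided overall error 0.05, power 80%, N = 232. From section 13.7: 58 per group at the interim and 116 per group at the end; accept at the interim if Z ≤ 0.48887, reject if Z > 2.31015 (2.31013 in the text, with no practical effect); final threshold 1.63351.

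**Step 1: reproduce the design.** The fixed one-sided sample size per group with unpooled variance is (1.645 + 0.842)² × (0.12×0.88 + 0.25×0.75) / 0.13² = 107.2. Integrating over the stated boundaries at half information gives an overall type I error of 0.0500 and a sample-size inflation factor of 1.073. Then 2 × 107.2 × 1.073 ≈ 230 (236 to 237 with pooled variance), within 3% of 232. Power at 116 per group is 80.3% (79.3% pooled). The design is sound on its own terms.

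**Step 2: a final result just inside the acceptance region.** This is a hypothetical result with an AED rate near 12%: 14/116 on AED and 23/116 without.

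- Difference: 0.1983 - 0.1207 = 0.0776.
- Pooled rate: 37/232 = 0.1595. Pooled standard error: √(2 × 0.1595 × 0.8405 / 116) = 0.0481. Z = 0.0776 / 0.0481 = 1.614, which is below 1.63351, so H0 is accepted.
- Unpooled standard error: √[(0.1207×0.8793 + 0.1983×0.8017) / 116] = 0.0478.
- 95% CI: 0.0776 ± 1.960 × 0.0478 = -1.6 to 17.1 points. 90% CI: 0.0776 ± 1.645 × 0.0478 = -0.1 to 15.6 points.
- With stage-wise ordering to allow for the interim look (normal approximation): 95% CI about -1.6 to 18.1; 90% CI about -0.1 to 16.5.

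Both levels include the 13-point design benefit. One more no-AED event (24/116) gives Z = 1.774, and the stated conclusion becomes that AED is better.

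**Step 3: how far this extends.** With 14/116 on AED, the accepted no-AED counts whose unadjusted upper limit reaches 13 points are 21 to 23 on the 90% interval and 19 to 23 on the 95% interval. At the interim, 7/58 versus 8/58 gives Z = 0.277 and is accepted. Its 95% CI is -10.5 to 13.9 points, but its 90% CI is -8.5 to 12.0 and excludes 13.

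**Step 4: how often.** This is an exact binomial calculation of the two-stage rule with AED at 12%. The no-AED rates of 18% and 20% are illustrative assumptions.

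| No-AED rate | P(accept) | P(accept and 90% CI reaches 13 points) | P(accept and 95% CI reaches 13 points) |
|---|---|---|---|
| 12% | 95.0% | 3.7% | 15.6% |
| 18% | 65.1% | 18.1% | 33.7% |
| 20% | 50.5% | 19.4% | 31.5% |
| 25% | 19.5% | 11.8% | 15.6% |

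The second column is ordinary type I and type II error behaviour and would be the same under any wording. The last two columns show how often the stated conclusion would accompany an interval that still allows the full design benefit.

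These joint probabilities depend on the AED rate. For an assumed true 8-point benefit they are 6% (90% CI) and 17% (95% CI) at an AED rate of 8%, 28% and 39% at 15%, and 38% and 48% at 20%.

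All of these calculations use the unstratified Z. The plan's stratified Cochran-Mantel-Haenszel statistic would shift individual cases slightly.

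**The case against.** Accepting the null is normal language for a design with a formal acceptance boundary, and the gloss correctly states θ ≤ 0. The boundary also carries information: it limits the chance of acceptance to about 20% when the true benefit is 13 points. A reader might therefore infer too much from this point, namely that a non-significant result says nothing beyond a failure to demonstrate benefit. The design does not support that. Acceptance is some evidence against a benefit as large as 13 points; it is not evidence of equality or harm.

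The 14 versus 23 example is the last accepted count before the boundary. The 90% interval is the one that matches a one-sided 5% test. On it, with AED at 12%, about 72% of acceptances exclude 13 points when the no-AED rate is 18% (1 - 0.181/0.651), and about 62% do at 20% (1 - 0.194/0.505). At 25% it is only about 39% (1 - 0.118/0.195). The interim wording is also less exposed, because section 13.7 describes that region through the observed percentages and the 7/58 versus 8/58 case excludes 13 points on the 90% interval. These points narrow the concern but do not remove it at the final analysis.

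Two further readings go beyond the documents. A reader might infer that the protocol commits to acting against prophylaxis whenever Z is non-significant. Section 5.2.9 is conditional, does not equate no difference with non-significance, and adds a weighing of risk and benefit. A reader might also infer that no confidence interval is planned. The SAP text available ends at the start of medical history, so its analysis sections cannot be checked.

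**Conclusion.** The concern holds as a matter of interpretation. Followed as written, section 13.7 yields a conclusion that its test does not support: Z at or below the boundary does not show that the groups are the same or that no AED is better. Smaller benefits may remain compatible with the data and, near the final boundary, so may the 13-point design benefit. With AED at 12%, the stated conclusion would accompany an interval still reaching 13 points in 11.8% of trials (90% CI) or 15.6% (95% CI) at the design effect, and in 19.4% or 31.5% if the no-AED rate were 20%. These figures assume the planned group sizes, an unstratified Z and unadjusted Wald intervals.

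Type I error, power, sample size and boundaries are unaffected. The correction should be made because it is cheap and bears on how the main result is read. Confidence is medium, since the SAP may contain an interpretation rule that could not be seen.

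**What to change.** 1. In the section 13.7 table footnote, the light blue region text and the interim conclusion, replace the statement that AED is not better, and its gloss, with: 'benefit of AED not demonstrated'.
2. Add one sentence saying that accept, accepted and acceptance in sections 13.4.2, 13.7 and 13.8 are stopping labels, not findings about the treatments.
3. Report P2 - P1 with a confidence interval that allows for the interim look, unless the SAP already plans one. Stage-wise ordering is one option.
4. In section 5.2.9, say that a claim of no difference rests on which benefits that interval excludes, not on non-significance alone.

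If the protocol can no longer be amended, use the same wording in the results report. The SAP already describes randomization and follow-up in the past tense, so this may be the practical route.

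The cost is three wording changes, one added sentence, one clause in section 5.2.9 and at most one extra interval. Sample size, boundaries and data collection stay as they are. The downside is that a non-significant result will support a weaker claim than the plan now makes.
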